3 THEORETICAL FRAMEWORK

Older patient with a GBM have an average prognosis of 3-6 months. Treatment options are universally palliative and should be aimed at improving or maintaining quality of life for the remainder of these patients' lives. Treatment decisions therefore need to be based around an informed conversation with the patient of the balance between survival benefit and side effect profile. Clinical trials have shown

efficacy of single agent radiotherapy or chemotherapy or short courses of concurrent chemoradiation. Molecular markers have been developed which can help guide decisions regarding the likely efficacy of chemotherapy however no such marker exist for decisions regarding radiotherapy.

Radiotherapy is an effective palliative treatment for GBMs and has been shown in clinical trials to maintain or improve health related quality of life. However outside of a clinical trial population, usual clinical practice reveals some patients in whom the side effect profile from cranial radiotherapy is intolerable and has a significant detrimental effect on patients' quality of life for their remaining short lifespan. The BRITER study aims to examine whether analysis of pre-treatment MRI scans in this cohort could help to predict who is more vulnerable to these side effects and therefore reveal a group of patients in whom single agent chemotherapy or best supportive care would be better treatment options.

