4 RESEARCH QUESTION/AIM(S)

4.1 Objectives

The BRITER study is being performed in patients aged 65 or over who have a new diagnosis of GBM. It tests the hypothesis that there is a relationship between 5 scores of a 'vulnerable' brain seen on pre-treatment MRI and a clinically significant change in patient quality of life, as defined by a 10 point change in the EORTC QLQ questionnaire from baseline to 8 weeks post treatment.

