- 3D volumetric inversion recovery or MP-RAGE (additional sequence - to allow accurate quantification of cortical thickness/volumes using Freesurfer software in addition to scoring methods of atrophy, must be acquired at 1mm or below)
- Axial T2* gradient echo (4mm slice thickness)

The scan thickness and sequences performed may vary slightly between sites however prior to opening the sites will confirm they can produce the necessary sequences for [name] to produce 5 quantitative scores (tumour volume, contralateral hemispheric brain volume, contralateral cerebral hemisphere cortical thickness, microhaemorrhage score and white matter hyperintensity score) from the images which reflect the degree of potential vulnerability of the brain to the side effects of radiotherapy. These will then be analysed in relation to the clinical questionnaires, steroid usage and grade 3-5 CTCAE radiotherapy toxicity score using SPSS. Multivariable logistic regression models will be fitted to look for significant ($P<0.05$) relationships between the 10 point change in EORTC QLQ quality of life questionnaires and the MRI parameters. Exploratory statistical analysis of the relationships between the MRI parameters and the secondary endpoints will be performed although the study is not powered to detect statistically significant relationships between these.

The creation of the database and statistical analysis of the results will be performed by the CI with the help of a research assistant.

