7.2 Sampling

7.2.1 Size of sample

Sample size calculations have been performed assuming a clinically significant end point of a 10 point change (SD=22.1 taken from the EORTC website reference guide) in EORTC QLQ questionnaire score between baseline and 8 weeks. Estimated sample size for one-sample comparison of proportion to hypothesized value assuming a 2 sided alpha of 0.05 and power of 0.9 gives a sample of

73. However, allowing for 20% attrition in questionnaire completion, this results in a sample size of 91. With 73 patients at 8 weeks, we will have 90% power for 5% significance to detect 5% of patients achieving a 10 point change in QoL. However, this small a proportion will only allow us to fit one variable in the model. It has therefore been recommended by the statistical team to aim for a recruitment target of 100 patients in order to fit the 5 MRI variables to the model.

Patients who are enrolled within CTIMP studies will not be eligible to be recruited into the study as they would introduce too many unknown variables for adequate statistical analysis with a cohort of this size.

Previous work done by this study group has shown this is a feasible recruitment target over 2 years.

The study team will review recruitment at 9 months and if it has not reached 25% then they will explore ways to increase recruitment, including opening at other sites.

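### The only power figure (90%, n = 73) belongs to a one-sample proportion test that has no stated null and is not planned; the primary five-score logistic regression has no power statement

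*Combined protocol and SAP*

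**What the plan says.** **Sizing (Section 7.2.1).** The method is "Estimated sample size for one-sample comparison of proportion to hypothesized value", two-sided alpha 0.05 and power 0.9, which gives 73. Allowing for 20% attrition gives 91. A 10-point change with an SD of 22.1 is quoted as the endpoint assumption. The power claim made for 73 completers at the 8-week assessment is: "we will have 90% power for 5% significance to detect 5% of patients achieving a 10 point change in QoL". The section then concedes that "this small a proportion will only allow us to fit one variable in the model" and reports statistical advice to "aim for a recruitment target of 100 patients in order to fit the 5 MRI variables to the model".

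**Hypothesis (Section 4.1).** The study tests for a relationship between five scores of a vulnerable "brain seen on pre-treatment MRI and a clinically significant change in patient quality of life".

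**Outcome (Section 4.2).** The primary outcome is the proportion of patients with a 10-point change from baseline to 8 weeks. No reference value is set.

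**Analysis (Section 5, closing paragraphs).** "Multivariable logistic regression models will be fitted to look for significant" relationships, at P<0.05, between the 10-point change and the MRI parameters. Analyses of the secondary endpoints are called exploratory, "although the study is not powered to detect statistically significant relationships between these".

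**The concern.** A one-sample test of a proportion needs a null value, an alternative, alpha and power. Section 7.2.1 gives alpha, power and one rate, and leaves out the other rate. The SD of 22.1 has no place in such a test. The 90% therefore cannot be traced to its inputs.

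The test that was sized is also not the test that will be run. The primary question is whether MRI scores are associated with the quality-of-life event. Power for that depends on the event rate, the odds ratio, the correlation between scores and the number of completers, and the plan gives only the last. Because Section 5 disclaims power for the secondary endpoints alone, a reader will take the primary association to be powered, and the only figure to hand is 90%. A null MRI result could then be reported as coming from a 90%-powered analysis when no power for that analysis has been worked out. This matters because Section 3 hopes the scores will identify patients for whom other treatment options would be better.

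**Working it through.** **1. Reproducing 73.** Standard formula, with p0 the null and p1 the true proportion:

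n = [(z₀.₉₇₅·√(p0(1−p0)) + z_power·√(p1(1−p1))) / (p1−p0)]²

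| Null p0 | True p1 | Result | Rates stated in the plan? |
|---|---|---|---|
| 5% | 0% | n = 72.99 at 50%, 80%, 90% and 99% power alike | 5% yes, 0% no |
| 0.36% | 5% | n ≈ 73 at 90% | 5% yes, 0.36% no |
| 16.9% | 5% | n ≈ 73 at 90% | 5% yes, 16.9% no |
| 1% | 5% | n = 141 at 90% | 5% yes, 1% no |
| 10% | 5% | n = 301 at 90% | 5% yes, 10% no |

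In the first row √(p1(1−p1)) = 0, so n = (1.96 × √(0.05 × 0.95) / 0.05)² = 72.99 and power has no influence. Read as worded (null 0%, true 5%), any single event rejects the null, so power at n = 73 is 1 − 0.95⁷³ = 0.976. Using 10 points and SD 22.1 in a one-sample test of a mean gives 52 (54 with the t distribution), not 73. The attrition step is sound: 73/0.8 = 91.25.

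**2. The step to 100.** With 20% attrition, 100 recruits give 80 completers. At a 5% rate, expected events are 0.05 × 73 = 3.65 and 0.05 × 80 = 4.0. For five scores that is 4.0/5 = 0.8 events per score. Moving to 100 adds 0.35 of an expected event.

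**3. What the planned model can detect.** The plan gives no event rate or effect size, so these are assumptions:

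- Five standardised normal scores, one associated with the event and four not; equal pairwise correlation of 0 or 0.5.
- Two-sided 0.05 Wald test of the associated score in the five-score model.
- Event rates of 20%, 32.5% and 50%. The middle value is P(Z > 10/22.1), taking 22.1 as the SD of change, a normal change with mean zero, and one direction only.
- 80 completers as planned, and 60 as a lower case. "Older patient with a GBM have an average prognosis of 3-6 months" (Section 3), and Section 7.3.2 withdraws participants who lose capacity, so losses above 20% are plausible.
- 6,000 simulated data sets per cell. With no association and 80 completers, rejection rates were 4.8%, 4.5% and 5.1%.

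Odds ratio per SD detectable with about 90% power:

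| Completers | Correlation | Rate 20% | Rate 32.5% | Rate 50% |
|---|---|---|---|---|
| 80 | 0 | 2.9 | 2.4 | 2.3 |
| 80 | 0.5 | 4.4 | 3.3 | 3.0 |
| 60 | 0 | 3.8 | 2.9 | 2.7 |

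Power for an odds ratio of 2 per SD:

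| Completers | Correlation | Rate 20% | Rate 32.5% | Rate 50% |
|---|---|---|---|---|
| 80 | 0 | 62% | 75% | 81% |
| 80 | 0.5 | 42% | 53% | 59% |
| 60 | 0 | 48% | 62% | 68% |
| 60 | 0.5 | 31% | 42% | 46% |

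At a 5% event rate, 80 completers give about 4 events (95% range 1 to 9), and about 10% of five-score data sets have no finite estimate because of separation. At 60 completers it is about 3 events and 24%.

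The usual normal approximation is optimistic here. It gives 2.47, 2.17 and 2.06 as the 90%-power odds ratios for 80 completers and uncorrelated scores; the simulated power at those values is only 81% to 83%.

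**The case against.** - **73 is not shown to be wrong.** True. Some pairs of rates give 73 at 90% power, and 91 follows from it. The fault is an unstated input and a mismatch between the sizing test and the analysis, not a slip in calculation.
- **The 90% is attached to the proportion, which is the named primary outcome, and Section 7.2.1 itself admits the limit on the model.** Both are correct. But estimating a proportion is not testing it, and no reference value or test is planned. The admission gives a reason for 100 without giving a power for the model fitted to those patients.
- **5% is a detectable proportion, not a forecast.** Fair as far as it goes. However, Section 7.2.1 draws its limit of one variable, and from that the move to 100, out of the 5% figure and offers no other rate. At minimum, the rate assumed for 100 is missing.
- **A per-score test is the reviewer's choice.** Section 5 looks for significant relationships with the MRI parameters, which supports it, but a joint test is possible. In simulation with 80 uncorrelated scores' data, a joint 5-df likelihood-ratio test has about 77% power at rate 20% and odds ratio 2.9, and about 74% at rate 32.5% and odds ratio 2.4. With correlated scores it can exceed the single-score test. Five uncorrelated scores each tested at 0.05 also carry about a 1 − 0.95⁵ = 23% chance of at least one false positive. The team should say which test decides.
- **Direction is not fixed.** Counting change both ways would make 32.5% about 65%. Relabelling event and non-event turns 65% into 35%, so the detectable odds ratio falls between the 32.5% and 50% columns.

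**Conclusion.** The concern holds. Three facts rest on the text alone: the null value is not stated, no one-sample test is planned, and no event rate, effect size or power is given for the primary regression. The plan's one power figure is therefore uncheckable and attached to the wrong analysis.

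The size depends on the stated assumptions. With 80 completers, about 90% power for one score needs an odds ratio per SD of roughly 2.3 to 2.9 if scores are uncorrelated and 3.0 to 4.4 at correlation 0.5. For an odds ratio of 2, power runs from 42% to 81%. At a 5% event rate the five-score model cannot be fitted reliably. This should be fixed, but it does not call the design, the sample size or the model into question.

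**What to change.** In Section 7.2.1:

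1. Remove the 90% power sentence, and the SD as an input to the proportion test, as justification for the primary analysis. If the one-sample figure is kept as description, state its null and alternative.
2. Say whether the primary hypothesis is judged per score or jointly.
3. State the detectable effect of the planned model at the expected number of completers, with assumptions labelled. For a per-score test, for example:

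> With 100 recruited and 20% attrition, 80 completers are expected; 60 is shown as a lower case. By simulation of the five-score model (two-sided 0.05, uncorrelated standardised scores), the odds ratio per SD for one score detectable with about 90% power is about 2.9, 2.4 and 2.3 at assumed event rates of 20%, 32.5% and 50% with 80 completers, and about 3.8, 2.9 and 2.7 with 60. Correlated scores need larger odds ratios (about 4.4, 3.3 and 3.0 at pairwise correlation 0.5 with 80). The event rates are assumptions; 32.5% assumes a normal change with mean 0 and SD 22.1, counted in one direction. At a 5% event rate (about 4 events) the five-score model cannot be fitted reliably.

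The SD then appears only as a labelled assumption behind one event rate. The team should substitute its own rates and correlations if it has them.

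Cost: rewording and one short simulation. Sample size, data collection and the planned model are unchanged. The stated power becomes less favourable.

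### Section 7.2.1 quotes an SD of 22.1 for the 10-point change but plans on 5% of patients reaching it; the SD is unused in the calculation and hard to reconcile with 5%

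*Combined protocol and SAP*

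**What the plan says.** Section 7.2.1 (Size of sample) opens its calculation by "assuming a clinically significant end point of a 10 point change (SD=22.1 taken from the EORTC website reference guide", and this is a change "in EORTC QLQ questionnaire score between baseline and 8 weeks". The test it names is a "one-sample comparison of proportion to hypothesized value assuming a 2 sided alpha of 0.05 and power of 0.9 gives a sample of"; the resulting figure is 73. An allowance of 20% for questionnaire attrition raises this to 91.

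The paragraph then restates the result: "With 73 patients at 8 weeks, we will have 90% power for 5% significance". The purpose of that power is "to detect 5% of patients achieving a 10 point change in QoL". The next sentence draws a consequence for the regression: "However, this small a proportion will only allow us to fit one variable in the model". On that basis the target becomes 100, so that five MRI variables can be fitted.

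Section 4.2 defines the primary outcome as the proportion of patients with a 10-point change, and section 5 sets the threshold at 10 points or more. Neither gives a direction. Section 5 makes multivariable logistic regression on the MRI scores the primary analysis. No section gives a null proportion, a source for the 5%, a correlation between the two time points, or an expected mean change.

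**The concern.** An SD for a change score and the share of patients passing a threshold on that score are linked. Ten points is only 10/22.1 = 0.45 of the quoted SD, and a cut-off that close to the centre of a distribution is normally passed by far more than 1 patient in 20. The paragraph sets the two figures side by side and does not connect them.

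The expected number of events governs what the logistic model can carry. If 5% is right, the study yields about 4 events from 80 completers for five MRI variables. If the SD is a fair guide, there are several times as many events, and the statement that only one variable can be fitted rests on the wrong figure. A reader of section 7.2.1 cannot tell which situation was planned for. Under the SD, a sizeable share of patients would also count as events with no average change in the cohort, which matters when the primary proportion is reported.

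**Working it through.** **Inputs from section 7.2.1.** Threshold 10 points; SD 22.1; proportion 5%; two-sided alpha 0.05; power 0.90; 73 evaluable; 20% attrition; target 100. Completers at the target: 100 × 0.80 = 80.

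**Assumptions, not in the documents.** Normally distributed change; mean change zero unless stated; a null proportion where one is needed; a correlation r where 22.1 is read as an SD at one time.

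**1. Reproduce the 73.** For one proportion,

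n = [(1.960·√(p0(1−p0)) + 1.282·√(p1(1−p1))) / (p1−p0)]².

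Only one proportion is stated. With p0 = 0.05 and p1 = 0 (assumed), n = 1.960² × 0.05 × 0.95 / 0.05² = 72.99, so 73. The power term vanishes in this case, and the result equals the n for a 95% interval of 5% ± 5 points. With p1 = 0.05, a null of about 0.36% would also return 73. Attrition: 73/0.8 = 91.25, consistent with the stated 91. The SD appears nowhere in this formula.

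**2. Share over the threshold if 22.1 is the SD of change.**

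- One given direction: 1 − Φ(10/22.1) = 32.5%.
- Either direction: 2 × 32.5% = 65.1%.

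**3. Share if 22.1 is the SD of scores at one time.** SD of change = 22.1 × √(2(1−r)).

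| Assumed r | SD of change | One way | Either way | Events in 80, one way | Events in 80, either way |
|---|---|---|---|---|---|
| 0.3 | 26.1 | 35.1% | 70.2% | 28 | 56 |
| 0.5 | 22.1 | 32.5% | 65.1% | 26 | 52 |
| 0.7 | 17.1 | 28.0% | 55.9% | 22 | 45 |
| 0.9 | 9.9 | 15.6% | 31.2% | 12 | 25 |

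The planned 5% gives 0.05 × 80 = 4 events, or 4/5 = 0.8 per MRI variable.

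**4. What 5% would require.**

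- Zero mean change, one way: SD of change = 10/1.645 = 6.08, so r = 1 − (6.08/22.1)²/2 = 0.96.
- Zero mean change, either way: SD of change = 10/1.960 = 5.10, so r = 1 − (5.10/22.1)²/2 = 0.97.
- SD of change kept at 22.1, one way: a mean shift of 1.645 × 22.1 − 10 = 26.4 points in the opposite direction.
- SD of change kept at 22.1, either way: no mean shift works, because any shift raises the share above 65% (68% at a 10-point shift).

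**5. Sensitivity, SD of change 22.1.** A 10-point mean shift in the opposite direction leaves 18% one way. Heavier tails at the same SD give 26% one way and 53% either way (Laplace), or 25% and 49% (t with 3 degrees of freedom).

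**The case against.** The strongest reply is that the two figures need not describe the same thing. The SD comes from an external reference guide, and the documents do not say whether it is an SD of change or of scores at one visit, nor which scale or population it belongs to. This stands. It is why the result is a range and why the first step of the fix is to identify the SD.

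A second reply is that 5% is worded as a proportion to detect, and a detectable value need not be the expected rate. That would be fair if the paragraph stopped there. But the following sentence says "this small a proportion will only allow us to fit one variable in the model", which uses 5% as the event rate available to the regression.

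A third is that any error is on the safe side: if the SD is right, there are more events than planned. This also stands, and it limits the consequence to the planning text.

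Stronger readings are tempting, and the documents do not support them. A reader might infer that the two inputs contradict each other by a fixed factor of 6 to 13 (32.5/5 and 65.1/5). That ratio holds only with normality, zero mean change and 22.1 as the SD of change. A reader might infer that the SD went into the 73. It did not need to, so it is a figure quoted alongside the calculation. Nor does a large share of events at zero mean change make those events noise: section 1 says that side effects and their effect on quality of life vary widely between patients, and explaining that variation is the study's purpose.

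**Conclusion.** The point holds in this form: section 7.2.1 quotes an SD that its calculation does not use and that is hard to reconcile with its planning proportion. Nothing elsewhere in the document reconciles them. Under normality and zero mean change, the SD implies about 16% to 35% of patients over the threshold one way and 31% to 70% either way, for assumed correlations of 0.3 to 0.9; reading 22.1 directly as the SD of change gives 33% and 65%. That is roughly 12 to 28 or 25 to 56 events among 80 completers, against 4 at 5%. Every alternative tried at plausible values stays well above 5%. Reaching 5% takes a correlation of 0.96 to 0.97 or, one way only, a mean shift of about 26 points in the opposite direction.

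The size of the gap depends on these assumptions; its direction does not. The documents alone do not show which of the two figures is wrong. What needs correcting is the planning proportion or the SD, and the statement about model capacity that rests on the proportion.

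**What to change.** In section 7.2.1, first state whether 22.1 is an SD of change or of scores at one time, and for which EORTC scale. Then do one of the following:

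- **(a) Keep the SD.** Replace the 5% and the one-variable sentence with an expected proportion and event count derived from that SD, for the direction of change that the endpoint uses. Show the correlation and mean-change assumptions as a range, not as single fixed values.
- **(b) Keep the 5%.** Cite its source, delete the unused SD, and state that it gives about 4 events among 80 completers, fewer than one per MRI variable.

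Option (a) needs the direction of the 10-point change to be stated, since sections 4.2 and 5 leave it open and the event count roughly doubles if both directions count.

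The cost is protocol wording and a check of the reference guide. Recruitment does not change.

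### Section 7.2.1: going from 91 to 100 recruits adds only 9.6% to expected events, so it cannot be what lets the model take five MRI variables instead of one

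*Combined protocol and SAP*

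**What the plan says.** Section 7.2.1 bases the calculation on this: "Estimated sample size for one-sample comparison of proportion to hypothesized value", with two-sided alpha 0.05 and power 0.9, and arrives at 73 patients. It then says that "allowing for 20% attrition in questionnaire completion, this results in a sample size of 91". With 73 patients at 8 weeks it claims "90% power for 5% significance to detect 5% of patients achieving a 10 point change in QoL". It adds the caveat that "this small a proportion will only allow us to fit one variable in the model". The next sentence draws the consequence: the statistical team has therefore advised the study to "aim for a recruitment target of 100 patients in order to fit the 5 MRI variables to the model".

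Section 4.1 states the hypothesis as a relationship between five MRI scores and a clinically significant change in quality of life, "as defined by a 10 point change in the EORTC QLQ questionnaire from baseline to 8 weeks post treatment". Section 5 names the five scores and the primary analysis: "Multivariable logistic regression models will be fitted to look for significant" relationships, at P<0.05, between the 10-point change and the MRI parameters. For the MRI parameters and the secondary endpoints, section 5 says that "the study is not powered to detect statistically significant relationships between these". It makes no such statement about the primary model.

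Sections 4.1, 4.2 and 5 do not say which score must move by 10 points, or whether only worsening counts.

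**The concern.** The final sample size rests on one inference: 91 recruits allow one variable, so recruit 100 and fit five. In a logistic model the number of variables that can be supported depends mainly on the size of the smaller outcome class. An increase of nine recruits barely changes that number, and the section gives no other event rate and no rule linking 100 to five variables.

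The five-score model is the test of the study hypothesis. The section gives a 90% power figure and then a sample size said to accommodate five variables, while section 5 disclaims power only for the secondary endpoints. A reader may conclude that the MRI associations are powered at about 90%. No calculation of that kind is given.

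**Working it through.** **Inputs from section 7.2.1:** 73 completers, 20% attrition, 91 recruits, final target 100, a proportion of 5%, one variable supported at that proportion, five wanted.

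**1. Reproduce the plan's figure.** Recruits = completers / (1 − attrition) = 73 / 0.80 = 91.25. The stated 91 agrees to within rounding. The 73 itself cannot be checked because the hypothesised proportion is not given; nothing below depends on how it was obtained.

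**2. Apply the same attrition to 100.** 100 × 0.80 = 80 completers. 80 / 73 = 1.096, so 7 more completers, or 9.6% more.

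**3. Expected events.** Events = completers × rate, so the ratio is 1.096 whatever the rate. At 5%: 73 × 0.05 = 3.65 and 80 × 0.05 = 4.0, a gain of 0.35 events.

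**4. How much depends on the rate.** All rates other than 5% are assumptions. The 33% and 65% come from an illustration: change normally distributed with mean zero, and 22.1 taken as the SD of change, which the plan does not say. Then 10 / 22.1 = 0.452, P(worse by 10 or more) = 0.325 and P(10 or more in either direction) = 0.651.

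The table sets the smaller outcome class beside simulated power for one score. Simulation assumptions: five standard-normal scores; correlation 0.3 among four of them; one of those four with a true odds ratio of 2 per SD; ordinary logistic fit; Wald P<0.05; failed fits counted as not significant; 2,000 runs per cell. The odds ratio and correlation are not in the documents.

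| Event rate | Smaller class, 73 | Smaller class, 80 | Power, 73 | Power, 80 | Failed fits, 80 |
|---|---|---|---|---|---|
| 5% | 3.65 | 4.0 | 9.2% | 12.9% | 10–13% |
| 10% | 7.3 | 8.0 | 28.8% | 31.4% | 0.4–1.0% |
| 20% | 14.6 | 16.0 | 50.9% | 55.2% | none |
| 33% | 24.1 | 26.4 | 64.3% | 67.4% | none |
| 65% (non-events are the smaller class) | 25.6 | 28.0 | 66.1% | 69.8% | none |

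Failed fits are given as a range over a true odds ratio of 1 or 2. Reading across a row, the step from 73 to 80 adds 2.6 to 4.3 percentage points. Reading down a column, the rate moves power from about 13% to 70% with 80 completers. With correlations from 0 to 0.5 and 80 completers, power runs 9–15%, 26–36%, 42–62%, 57–76% and 58–76% down the rows.

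**5. Spurious effects.** With no true effect and 80 completers, an odds ratio above 2 or below 0.5 appears in 35% of converged fits at 5%, 18% at 10%, 7% at 20% and 2.5–3% at 33–65%.

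**6. Firth penalisation, 80 completers.** The mean absolute log odds ratio under no effect is 0.47 instead of 0.66 at 5%, and 0.34 instead of 0.42 at 10%. Power is 17% at 5%, 31% at 10%, and within 1 point of the ordinary fit at 20–65%.

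**The case against.** The best defence is that the one-variable limit is tied to 5%, and 5% is a detectable proportion, not a forecast. On that reading the five-variable target presumes a higher rate, and 100 is a margin above the minimum of 91. Much of this stands. The section contains no wrong sum, and at higher rates five scores can be fitted. But the text presents the larger target as the consequence of the one-variable limit and as the means of fitting five. If a higher rate is what makes five variables possible, that rate is the missing assumption. The statistical team may have working for 100, but neither the rate nor the working is in the document.

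It can also be said that section 7.2.1 already describes the 90% as power for a one-sample proportion. That is right. What is missing is a statement that it does not carry over to the MRI associations.

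Two stronger readings are tempting and should be resisted. A reader might infer that about four events are expected and that 100 patients are therefore too few. The documents do not support that, because 5% is not offered as the expected rate. A reader might also back-calculate a rule: if 3.65 events allow one variable but not two, the requirement is 3.65 / 2 = 1.83 to 3.65 events per variable, or about 9 to 18 events for five. This is a reader's construction. The plan states no events-per-variable rule and none should be attributed to it.

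Finally, penalised fitting is partly a matter of preference. It matters mainly when the smaller class is small, and changes little at about 16 or more.

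**Conclusion.** The point holds as a defect in the sample-size justification, and it should be fixed. By the plan's own attrition, the move from 91 to 100 recruits is a move from 73 to 80 completers. That result needs only the assumption that the 20% attrition and the event rate are the same at both targets. It cannot account for going from one variable to five; only an event rate well above 5% could, and none is stated. Nor can a rate be inferred, since the qualifying score and direction are undefined.

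No power is given for the five-score model. The simulated figures show only how strongly its performance depends on the rate. They rest on an assumed odds ratio, assumed correlations and normally distributed scores, and are not a forecast for this study. Whether 100 is adequate is left open.

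**What to change.** In section 7.2.1:

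1. State that 100 recruits give about 80 completers, and remove the implication that going from 91 to 100 allows five variables instead of one.
2. Define which score and which direction of 10-point change make an event. Then state the assumed event rate and its source.
3. Show the smaller outcome class among 80 completers at rates labelled as assumed: 4 at 5%, 8 at 10%, 16 at 20%, 26 at 33%, 28 at 65%. Make the five-score claim conditional on that class reaching a minimum that the statistical team chooses and justifies. If it is not reached, report the five-score results as exploratory.
4. Add that the 90% power does not apply to the MRI associations.

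Optional safeguard, in section 5: prespecify Firth-penalised logistic regression with profile-likelihood intervals, at least for the case where the smaller class falls below the chosen minimum. It reduces inflated estimates and failed fits. It does not restore power, and the text should say so.

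The cost is protocol wording and a less favourable stated basis for the sample size. No new patients or data are needed. The Firth option may need software beyond base SPSS.
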